7.1. Screening process differences for each Arm

Investigational Plan, Protocol CT-05 (Extension Study)

Document #: CT-4

Rev: 1.0

Effective: 11/24/2021

All subjects were screened for the eligibility criteria in Sections 7.2 and 7.3 upon entry to The RESTFUL Study, with the exception of IC #13 and EC #25-27. The following subset of eligibility criteria will be re-assessed at screening for CT-05, to confirm that they still apply:

- **Arm 1:** IC #8, 12-13. EC #7, 11*, 12, 14-17, 19, 21-27.
 - * except that acute infections with mild symptoms will not be exclusionary.
- Arm 2: IC #12-13. EC #12, 17, 21, 23, 25.
- **Arm 3:** IC #3-8, 10, 12-13. EC #2, 3, 6-12, 14-17, 19-27.

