7.2. Complete list of inclusion criteria (IC)

All subjects are required to meet the following inclusion criteria in order to be considered eligible for participation in this study:

- 1. Subject has received a medical diagnosis of primary restless legs syndrome (RLS).
- 2. Subject is refractory to RLS medication (as defined in section 7.3).
- 3. Subject has moderate-severe RLS symptoms as defined by a score of 15 or greater points on IRLS (International Restless Legs Syndrome Study Group Rating Scale [12]) over the week prior to study entry.
- 4. Subject has RLS symptoms 2 or more nights per week during the week prior to study entry as defined by a score of 2, 3, or 4 on IRLS question #7.
- 5. RLS symptoms are most significant in the subject's lower legs and/or feet.
- 6. RLS symptoms are most significant at bedtime, after bedtime, and/or in the 2 hours before bedtime.
- 7. RLS symptoms between 10am and 6pm are not severe.
- 8. Subject agrees to not change dosage or schedule of any medications that are known to impact RLS symptoms during the study, including RLS medications, antidepressants, sleep medications, or sedative antihistamines.
- 9. Subject agrees to not make major lifestyle changes during the study that would significantly affect bedtime, such as major changes to diet, exercise, or career.

Investigational Plan, Protocol CT-05 (Extension Study)

Document #: CT-4

Rev: 1.0

Effective: 11/24/2021

- 10. Subject possesses the necessary equipment, internet/phone accessibility, and communication ability to complete electronic questionnaires and respond to electronic communications and phone calls from the research staff throughout the in-home portion of the study.
- 11. Subject is \geq 22 and \leq 79 years of age when written informed consent is obtained.
- 12. Subject has signed a valid, IRB-approved informed consent form, can understand the requirements of the study and instructions for device usage, and can converse in English.
- 13. Subject previously completed the RESTFUL Study.

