Evaluation 7: (20-wks after Eval #1) Phone follow-up to assess RLS symptoms, NTX100 use, and assess the occurrence of adverse events and/or changes to daily medications.

Evaluation 8: (24-wks after Eval #1) In-person follow-up to assess RLS symptoms, NTX100 use, and assess the occurrence of adverse events and/or changes to daily medications. Devices are returned at this time.

Evaluation 9: (32-wks after Eval #1) Phone follow-up to assess RLS symptoms, adverse events, and any changes to daily medications. Study exit occurs at this time.

* See Section 16.13 below for discussion of device replacement and in-person visits.

In addition to these assessments, subjects will complete a Weekly Questionnaire each week throughout the 24-wk duration of device usage and a Bi-weekly Questionnaire every 2-weeks from Weeks 25-32.

The schedule of assessments are shown in Table 4 below. Additionally, the devices may automatically log quantitative compliance, usage data, and leg movement data throughout the duration of the study.

Table 4. Schedule of Assessments for Arms 1 and 3

Investigational Plan, Protocol CT-05 (Extension Study)

Document #: CT-4

Rev: 1.0

Effective: 11/24/2021

		Eval 1 Day 0	Wks 1-24	Wks 25-32	Eval 2 Wk-2	Eval 3 Wk-4	Eval 4 Wk-8 In-person or	Eval 5 Wk-12	Eval 6 Wk-16 In-person or	Eval 7 Wk-20	Eval 8 Wk-24	Eval 9 Wk-32
		In-person	Remote	Remote	Remote	Remote	Remote**	Remote	Remote**	Remote	In-person	Remote
Assessment	Completed by											
Screening		X										
Consent		X										
Study entry												
questionnaire	Staff + subject	X										
Weekly questionnaire	Subject		X									
Biweekly questionnaire	Subject			X								
Review weekly												
questionnaire												
responses	Staff				X	Х	X	Х	X	Х	X	
ConMeds	Staff	X			X	X	X	Х	X	Х	X	X
AE Monitoring/Reporting	Staff				Х	Х	X	X	X	X	X	X
RLS	Staff + subject	X (Arm 3 only*)			X	X	X	X	X	Х	X	X
PGI-I	Staff + subject				X	Х	X	X	X	Х	X	X
CGI-I	Investigator + subje	ect					X		X		Х	X
MOS-Sleep	Staff + subject	X (Arm 3 only*)				X	X	Х	Х	Х	Х	X
SF-36	Staff + subject	X									Х	
Device completion												
questionnaire	Staff + subject										X	
Study exit questionnaire	Staff + subject											X
Device replacement Sta	Staff + subject	X **					X **		X **			
		* For Arm 1, data	from Eval	11 of the RE	STFUL Stu	dv will be	used, since bo	th Evals	typically occ	ur on the	same day	

Arm 2:

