16.15. Study Exit

Study exit will occur at the conclusion of Eval #9. At study exit, the Investigator/coordinator will complete the study exit eCRF. Adverse events unresolved at study exit will be followed by the Investigator until resolution occurs or at least 30 days after the subject's participation in the study is complete.

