16.16. Subject Discontinuation

A subject may be removed from the study prior to completion for any of the following reasons:

- Voluntary withdrawal of consent
- Adverse event preventing further study participation
- Investigator believes risk of further subject participation outweighs benefit
- Persistent non-compliance or lost to follow-up
- Pregnancy
- Subject no longer meets inclusion criteria
- [For arms 1 and 3 only] Subject makes a significant change to dosage of medications known to interfere with sleep or RLS symptoms, including sleep medications, antidepressants, sedative antihistamines.

Investigational Plan, Protocol CT-05 (Extension Study)

Document #: CT-4

Rev: 1.0

Effective: 11/24/2021

• [For arms 1 and 3 only] Insufficient device availability (see 16.16.1 below)

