16.16.1. Discontinuation related to device availability

As noted in Section 11, the investigational device may include components that are consumable or semi-consumable and may be replaced on a periodic or as-needed basis. In the unlikely event that investigational device supply becomes insufficient to replenish the consumable components of the devices for all subjects enrolled in the study, enrollment will be paused and device replacement will continue in a normal manner until the device supply for the study is exhausted (or nearly exhausted). At that point, remaining subjects will be removed from the study at their next scheduled device replacement timepoint.

Additionally, it is possible that some patterns of device use or misuse may lead to a reduction in the functional lifespan of the investigational device below 8-weeks. If this is suspected for a specific subject, that subject may be removed from the study.

The Investigator or research staff will complete a study exit form in the eCRF for any subject who prematurely discontinues from the study. If discontinuation was the result of an AE, the AE will also be recorded in the eCRF.

Upon discontinuation, subjects will receive partial compensation commensurate with their completed Phases.

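### Protocol 16.16 lets device-arm subjects be removed from the study for a medication-dose change with no later efficacy assessment specified, so their Week 24 values are carried forward while Arm 2 medication changers are observed

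*Protocol*

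**What the plan says.** Protocol 16.16 opens with "A subject may be removed from the study prior to completion for any of the following reasons". One reason applies to the device arms alone: "For arms 1 and 3 only] Subject makes a significant change to dosage of medications known to interfere with sleep or RLS symptoms". The bullet then names sleep medications, antidepressants and sedative antihistamines. RLS drugs are not named, although the general wording can include them.

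A second reason in the same list is "Subject no longer meets inclusion criteria". Inclusion criterion #8 (Protocol 7.2) reads "Subject agrees to not change dosage or schedule of any medications that are known to impact RLS symptoms during the study". Protocol 7.1 lists it among the criteria checked again for Arm 1 ("IC #8, 12-13. EC #7, 11*, 12, 14-17, 19, 21-27") but not for Arm 2.

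After early discontinuation, Protocol 16.16.1 asks for paperwork: "The Investigator or research staff will complete a study exit form in the eCRF for any subject who prematurely discontinues from the study". Protocol 16.15 adds safety follow-up: "Adverse events unresolved at study exit will be followed by the Investigator until resolution occurs". Neither section names a CGI-I, PGI-I, IRLS or MOS-Sleep assessment at or after removal.

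Arm 2 is treated differently. SAP 3.1 and 3.2 allow its subjects to change RLS medication, and the Arm 2 schedule in Protocol 16.12 has CGI-I, PGI-I, IRLS and MOS-Sleep at Week 24.

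SAP 6.1 keeps every eligible enrolled subject in ITT. SAP 5.3 and 8.1 fill missing efficacy values by last observation carried forward (LOCF), and SAP 5.3 goes back to CT-04 when there is no value from this study.

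**The concern.** Changing a drug, or stopping the device, is no reason to stop collecting outcomes. Removal from the study creates a missing Week 24 value that the schedule could have supplied.

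The consequence differs by endpoint. The primary endpoint and key secondary endpoints #1-5 use Arm 1 alone, so there it means carried values in place of observed ones. Endpoints #6-11 compare Arm 1 with Arm 2 at Week 24. In that comparison, an Arm 1 subject removed after a medication change contributes a value from before removal, while an Arm 2 subject who changed medication contributes the value seen at Week 24. The two arms then measure different things in the subjects whose treatment changed.

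The SAP covers only Arms 1 and 2, so the analytical effect falls on Arm 1. Removal also cuts short the Arm 1 side of the SAP 9.0 summary of changes to RLS management over Weeks 1 to 24.

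**Working it through.** The plan states no removal rate, response rate or sample size (SAP 3.4), so there is no figure of its own to reproduce.

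**1. Age of the carried value.** Inputs are the visits before Week 24 in Protocol 16.12, Table 4: CGI-I at Weeks 8 and 16; PGI-I and IRLS at Weeks 2, 4, 8, 12, 16 and 20; MOS-Sleep at Weeks 4, 8, 12, 16 and 20. Age at Week 24 = 24 − week of the last assessment before removal. A CT-04 value counts as 24 weeks old, because CT-04 completion and Arm 1 entry typically fall on the same day.

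| Removal between weeks | CGI-I | PGI-I, IRLS | MOS-Sleep |
|---|---|---|---|
| 0-2 | 24 | 24 | 24 |
| 2-4 | 24 | 22 | 24 |
| 4-8 | 24 | 20 | 20 |
| 8-12 | 16 | 16 | 16 |
| 12-16 | 16 | 12 | 12 |
| 16-20 | 8 | 8 | 8 |
| 20-24 | 8 | 4 | 4 |

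CGI-I is older than PGI-I and IRLS for removals in 2 + 4 + 4 + 4 = 14 of the 24 weeks, by 2 or 4 weeks, and equally old in the other 10. If removal were uniform over the 24 weeks (an assumption), the mean ages would be:
- CGI-I: (8×24 + 8×16 + 8×8)/24 = 16.0 weeks
- PGI-I and IRLS: (2×24 + 2×22 + 4×20 + 4×16 + 4×12 + 4×8 + 4×4)/24 = 13.8 weeks
- MOS-Sleep: 4×(24 + 20 + 16 + 12 + 8 + 4)/24 = 14.0 weeks

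Medication changes are asked about at six follow-ups before Week 24. Four of them (Weeks 2, 4, 12 and 20) have no CGI-I. The Week 20 contact is one: "20-wks after Eval #1) Phone follow-up to assess RLS symptoms, NTX100 use, and assess the occurrence of adverse events and/or changes to daily medications". A change found there can come with a same-day PGI-I and IRLS, but the CGI-I to carry is the one from Week 16.

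**2. Possible size.** Shift in Arm 1 responder rate = share removed × (carried response rate − Week 24 response rate in those subjects). Shares and gaps are assumptions.
- Gap ±0.20: 0.05, 0.10 and 0.15 × ±0.20 = ±1, ±2 and ±3 points.
- Larger gap of 0.3 to 0.5 with 10% removed: 3 to 5 points.

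For scale, the 95% interval half-width at an assumed 60% response rate is 1.96 × √(0.24/40) = 15.2 points at n = 40 and 1.96 × √(0.24/80) = 10.7 points at n = 80.

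For #6 and #7, suppose both arms truly respond at 50% and the Arm 1 rate is shifted upward by 3 or 5 points. The one-sided 0.025 two-proportion test then rejects 4.2% or 5.8% of the time at 30 per arm, and 5.1% or 7.9% at 60 per arm. A downward shift would push rejection below 2.5%.

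**3. Do the supportive sets recover the value?**
- Per Protocol (SAP 6.3) excludes anyone who discontinued, so a removed subject leaves that set.
- Stable Medication (SAP 6.2) is used only for #6-11. It excludes subjects with new or changed RLS or sleep prescriptions. A subject removed for an antidepressant change alone stays in it with a carried value.

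Neither set contains the missing Week 24 outcome.

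**The case against.** The strongest reply is that this may rarely or never happen. Removal is discretionary. SAP 6.3 lists an Arm 1 RLS-medication change separately from discontinuation, the Stable Medication set screens for changes through Week 24, and SAP 9.0 tabulates them over the same period. All of this suggests that some changers are expected to stay. That stands, and it limits the size of the point.

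Second, the SAP already recognises the different medication instructions and answers them for #6-11 with the Stable Medication analysis. That stands in part. The set removes most changers from both arms but cannot supply their outcomes, and it does not apply to the primary endpoint or #1-5.

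Third, the age of a carried CGI-I is a feature of LOCF for any dropout. That is also true. It shows what a removal costs and is not a separate fault.

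A reader might go further in four ways that the documents do not support:
- *Arm 1 subjects who change RLS medication must be removed.* Protocol 16.16 says they may be, and its bullet does not name RLS drugs. The route through criterion #8 is only arguable, since that criterion is an agreement given at entry and re-assessed at screening.
- *The rule favours the device.* The change may be up or down, a subject who raises a dose may already be a non-responder, and added medication may work.
- *The primary endpoint suffers from an imbalance between arms.* It and #1-5 are single-arm.
- *Removed Arm 1 subjects should be counted as non-responders.* Doing so in Arm 1 only would add a new asymmetry, and it would score as a failure someone who cut a dose because the device helped.

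**Conclusion.** The point holds as a cheap, avoidable loss of data. Protocol 16.16 permits removal from the study, and not only from the device, for a significant medication-dose change in Arms 1 and 3, and no later efficacy assessment is specified. That none takes place is inferred from what Protocol 16.15 and 16.16.1 require; no sentence forbids one.

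For each Arm 1 subject so removed, the primary endpoint and #1-5 use a carried value, and #6-11 also acquire missingness that Arm 2 does not have. The carried CGI-I is 8, 16 or 24 weeks old.

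How often this happens, and in which direction it acts, is unknown. Under the smaller assumed gap the shift is 1 to 3 points, well inside a half-width of 10.7 to 15.2 points. Only larger assumed gaps make it matter for the between-arm tests. The change is worth making because it costs little, not because a material bias has been shown.

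**What to change.** In Protocol 16.16, replace the medication-change bullet with: *A medication change is recorded as a deviation; device use may continue or stop at the investigator's discretion, and scheduled evaluations continue through Eval 8 (Week 24).* Add that such a change does not by itself trigger removal under "Subject no longer meets inclusion criteria". Leave the other reasons for removal as they are.

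No new SAP imputation rule is needed. The existing ITT rule will use the observed Week 24 values, and Per Protocol and Stable Medication remain as the analyses that exclude most changers.

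In the Arm 1 completion table, report the number and week of any removals for medication change. SAP 9.0 promises completion rates but does not ask for this in its text; the table shell is not shown, so it may already be there. Protocol 13.6 already expects reasons for non-completion to be recorded.

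The cost is two protocol sentences, one table row, and at most Evals 2 to 8 for each affected subject, all already scheduled. Of these, only Eval 8 is listed as in-person with no remote option, and Protocol 18 allows remote substitution where necessary. The downside is that some ITT values will reflect changed medication.

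SAP 3.4 describes enrollment in the past tense. If follow-up has closed, the reporting change is the part that can still be made.

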16.16.1. Discontinuation related to device availability

As noted in Section 11, the investigational device may include components that are consumable or semi-consumable and may be replaced on a periodic or as-needed basis. In the unlikely event that investigational device supply becomes insufficient to replenish the consumable components of the devices for all subjects enrolled in the study, enrollment will be paused and device replacement will continue in a normal manner until the device supply for the study is exhausted (or nearly exhausted). At that point, remaining subjects will be removed from the study at their next scheduled device replacement timepoint.

Additionally, it is possible that some patterns of device use or misuse may lead to a reduction in the functional lifespan of the investigational device below 8-weeks. If this is suspected for a specific subject, that subject may be removed from the study.

The Investigator or research staff will complete a study exit form in the eCRF for any subject who prematurely discontinues from the study. If discontinuation was the result of an AE, the AE will also be recorded in the eCRF.

Upon discontinuation, subjects will receive partial compensation commensurate with their completed Phases.

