The investigational device may include components that are consumable or semi-consumable and may be replaced on a periodic or as-needed basis. Such device component replacement may occur via an in-person exchange or via delivery to the subject. At entry to Arm 1, subjects may continue using investigational device components from the RESTFUL Study prior to replacement – which may require one additional visit for in-person exchange or may be conducted via delivery to the subject.

Investigational Plan, Protocol CT-05 (Extension Study)

Document #: CT-4

Rev: 1.0

Effective: 11/24/2021

Typically, at Evals 4 and 6, stimulation unit replacement will occur and device log data will be downloaded to assess quantitative compliance and usage data and follow-up with the subject regarding usage data. To facilitate this process, subjects will be encouraged to attend an in-person visit. For subjects who live further from the site and/or cannot easily travel to the site, replacement device components will be delivered to the subject and the subject will return used stimulation units to the site for device log data analysis. For these subjects, the Eval may be split into two parts, where the second part is conducted upon receipt of stimulation units at the site and involves a call to follow-up with the subject regarding usage data.

Each time new stimulation units are provided to a subject during this study, they must be programmed with the specific calibrated settings corresponding to that subject.

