17.2.3. Efficacy Analysis

A Statistical Analysis Plan (SAP) will be developed prior to completion of the first subject in Arm 1 or 3, which will include a plan for efficacy analysis. The following analyses are planned:

- Primary statistical analysis may be conducted separately for subjects in Arms 1 and Arm 3.
 Additional pooled analysis across Arms 1 and 3 may also be conducted.
- Subgroup analysis form Arms 1 and 3 may be conducted based on the following criteria:
 - o Responders at Week-8 of The RESTFUL Study, as defined by CGI-I of 1 or 2.
 - o Non-responders at Week-8 of The RESTFUL Study, as defined by CGI-I of 3 or above.
- Missing data may be addressed with the use of multiple imputation.
- Appropriate statistical techniques will be employed to test statistical significance.
- If there is success on the primary endpoint, then secondary endpoints will be tested in order,
 according to the fixed-sequence method, until failure.

The analysis cohort for the primary efficacy endpoint are subjects who are enrolled and undergo the assigned treatment.

The Per Protocol analysis will exclude subjects for whom one or more of the following apply:

- 1. Dropout or removal from the study.
- 2. Incomplete or missing data for the endpoint.

Clinical Trial

Investigational Plan, Protocol CT-05 (Extension Study)

Document #: CT-4

Rev: 1.0

Effective: 11/24/2021

- 3. Clinically significant change in dose or schedule of medication that affects RLS symptoms.
- 4. New medical information available after randomization indicates an exclusion criterion.
- 5. Other protocol deviation occurs that is deemed clinically significant by the investigator.
- 6. Device usage at or after bedtime on fewer than two-thirds of the nights with RLS symptoms at or after bedtime, as reported by the subject on the Weekly Questionnaire assessments.
- 7. Missing two or more follow-ups (Follow-ups completed out-of-window are not considered "missing")
- 8. Zero total device uses.

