5.3 Handling of Dropouts and Missing Data

If there are any missing data for efficacy endpoints, the "Last Observation Carried Forward" imputation method will be used to impute the missing data. If no data are available in this study, then the last observation from CT-04 will be carried forward.

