8.0 EFFICACY AND SAFETY ANALYSES

8.1 Primary Efficacy Endpoint Analysis

The primary efficacy endpoint is the response on the Clinical Global Impressions-Improvement (CGI-I) scale at Week 24 of Arm 1 relative to Baseline (RESTFUL study entry) where a "successful" response is defined as a response of "Much Improved" or "Very Much Improved". This endpoint will be summarized by treatment group using frequencies and percentages.

The 95% confidence interval will be presented for the proportion of "successful" responses. If there are any missing data for this endpoint, last observation carried forward (LOCF) methods will be used to impute the missing data.

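### LOCF can count an old on-device CGI-I or PGI-I as Week 24 response for Arm 1 subjects removed early, and no planned analysis scores those subjects as failures

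*Protocol*

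**What the plan says.** Protocol 16.16.1 gives two device-related removal routes for Arms 1 and 3.

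- **Suspected wear.** If a pattern of use seems to cut device life below 8 weeks, "If this is suspected for a specific subject, that subject may be removed from the study". This is discretionary and can happen at any time.
- **Stock exhaustion.** The protocol calls this unlikely. If it happens, "remaining subjects will be removed from the study at their next scheduled device replacement timepoint". Protocol 16.13 places those time points: "Typically, at Evals 4 and 6, stimulation unit replacement will occur and device log data will be downloaded". Evals 4 and 6 are Weeks 8 and 16.

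For a premature exit, 16.16.1 requires a study exit form. It names no CGI-I or PGI-I at exit and no efficacy follow-up afterwards.

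SAP 6.1 puts all enrolled eligible subjects in ITT, the primary population for every efficacy endpoint. SAP 5.3 applies LOCF to any missing efficacy value and adds: "If no data are available in this study, then the last observation from CT-04 will be carried forward". SAP 8.1 repeats the rule for the primary endpoint: "If there are any missing data for this endpoint, last observation carried forward (LOCF) methods will be used to impute the missing data". The per-protocol population (SAP 6.3) excludes anyone who discontinued. The Stable Medication population (SAP 6.2) selects on medication change and leaves the LOCF rule alone.

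**The concern.** The stated objective is longer-duration efficacy. Under these rules, a subject with no CT-05 CGI-I at all, or none after Week 8, can enter the ITT analysis as a Week 24 responder. The wear route shows this most clearly. Its threshold is a device life under 8 weeks and the first CT-05 CGI-I is at Week 8, so removal can come before any CT-05 CGI-I exists. It is one instance of a general gap, because every Arm 1 removal under Protocol 16.16 reaches the same LOCF rule.

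Four results are affected: the primary CGI-I responder rate, key secondary #1 (PGI-I), and the Arm 1 versus Arm 2 responder comparisons #6 and #7. As planned, a reader of the summary tables could not tell how much of the 24-week rate was observed at 24 weeks. Nor does the plan say whether Week 24 is meant as response on device, status after stopping, or failure once removed.

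**Working it through.** **1. Age of the carried rating.** Age = 24 minus the week of the last rating. The CT-04 exit rating is taken as CT-05 Day 0, because Protocol 16.12 says RESTFUL Eval 11 and Arm 1 Eval 1 typically share a visit. Protocol Table 4 schedules the Arm 1 CGI-I at Weeks 8, 16, 24 and 32. A CT-04 Week 8 CGI-I exists, since Protocol 17.2.3 defines a subgroup by it: "Responders at Week-8 of The RESTFUL Study, as defined by CGI-I of 1 or 2".

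| Arm 1 removal | CGI-I carried | Age at Week 24 |
|---|---|---|
| Before the Week 8 rating | CT-04 Week 8 | 24 − 0 = 24 weeks |
| After Week 8, before the Week 16 rating | CT-05 Week 8 | 24 − 8 = 16 weeks |
| After Week 16, before Week 24 | CT-05 Week 16 | 24 − 16 = 8 weeks |

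Visit windows move these by days. All three ratings are on device. By Protocol 16.1, the CT-04 rating follows 4 or 8 weeks of active use, depending on the RESTFUL assignment. A stock removal at Eval 4 or 6 falls on a scheduled CGI-I, so its carried rating is normally 16 or 8 weeks old. It would be 24 or 16 only if that visit's rating were missed.

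PGI-I is also rated at Weeks 2, 4, 12 and 20. The CT-04 fallback then applies only to removal before Week 2 (24 weeks). Later removals carry a rating 22, 20, 16, 12, 8 or 4 weeks old.

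**2. Size.** SAP 3.4 makes no sample size determination, and neither document states a removal rate. There is no plan figure to reproduce, and every input below is an assumption.

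- One credited subject moves the ITT rate by at most 100/N: 3.3, 2.2, 1.7 and 1.1 points for N = 30, 45, 60 and 90.
- LOCF minus removals-as-failures = p × r, where p is the share removed and r the share of those carrying a response. For p = 5%, 10% and 20%, this is 2, 4 and 8 points at r = 40%, and 3, 6 and 12 points at r = 60%.
- If the intended status is the one after stopping, with responder rate s, the expected shift is p × (r − s). At s = 20% it is 1, 2 and 4 points for r = 40%, 2, 4 and 8 for r = 60%, and zero for r = 20%. If response on device is intended, this formula does not measure bias.
- For scale, the 95% CI half-width at a 60% rate is 196 × √(0.24/N): 17.5, 14.3, 12.4 and 10.1 points for N = 30, 45, 60 and 90. It would take 6, 7, 8 and 10 credited subjects to match it.

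**3. Would the per-protocol table show it?** Take N = 80, 8 removed, 50 responders among 72 completers, and 6 of the 8 carrying a response. LOCF gives 56/80 = 70.0% (exact 95% CI 59% to 80%). Per protocol gives 50/72 = 69.4%. Removals as failures gives 50/80 = 62.5% (51% to 73%). Dropping removed subjects can agree closely with LOCF and still say nothing about the lower bound.

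**The case against.** Several points on the other side stand.

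- **Few subjects are likely to be affected.** Exclusion criteria 26 and 27 screen out subjects who misused devices or had unusual malfunction rates in RESTFUL. Components can be replaced, and stock exhaustion is called unlikely.
- **Supply exits are administrative.** Protocol 17.4, on compliance, lists lack of device availability among reasons unrelated to response. Scoring those subjects as failures is a bound, not an estimate.
- **Outputs already planned cover part of this.** SAP Table 2.2 gives the per-protocol primary result, Table 3.1 the Arm 1 completion rates, and Listings 2.1, 2.2 and 5.2 the by-subject ratings and completion. A removals-as-failures rate could probably be rebuilt by hand from the listings, but no table presents it.
- **LOCF acts in both arms.** An Arm 2 subject with no CT-05 rating also carries a CT-04 on-device rating. If that is better than off-device status, it raises the control rate and works against the device in #6 and #7.

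A reader might infer more than this: that every removal carries a 24-week-old rating, that LOCF inflates the primary result, or that the wear rule lets poor responders be removed. The documents support none of these. Age depends on timing and route. LOCF favours the device only if the carried ratings are better than the status intended at Week 24. The wear rule turns on device life and pattern of use, not on response, although its discretion means that independence from outcome cannot be assumed either.

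**Conclusion.** The chain from removal to carried-forward response holds on the text. An on-device CGI-I 8 to 24 weeks old can count as Week 24 response. The 24-week case belongs mainly to wear removals before Week 8, and no planned analysis scores removed subjects as failures. How many subjects this affects cannot be derived and is probably small. The gap of 2 to 12 points over the ranges shown rests wholly on assumed removal shares and carried response rates, and only the highest values approach or exceed the narrowest CI half-width listed.

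This does not threaten the main result. The primary endpoint is reported with a 95% CI and no test, and the direction of any bias is undetermined until the intended Week 24 status is stated. It is a minor gap in sensitivity analysis that is cheap to close.

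**What to change.** In SAP 5.3 and 8.1, keep LOCF as the main method and add one sensitivity analysis of the CGI-I and PGI-I responder rates (primary, key secondary #1, #6 and #7) that counts Arm 1 subjects removed before Week 24 as non-responders. Show it twice: once for all removals, as a lower bound, and once with supply-exhaustion removals left under LOCF, consistent with Protocol 17.4. Arm 2 keeps LOCF, so state that for #6 and #7 the result is a bound against the device.

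Alongside it, tabulate by arm and removal reason how many Week 24 values were carried forward and from which week. Include Arm 2 subjects who carry a CT-04 on-device rating.

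The cost is one extra table from data already held, and possibly a less favourable sensitivity rate.

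Following removed subjects off device and entering those ratings in the ITT Week 24 rate is not recommended. It would need the Arm 1 stable-medication rule lifted and would mix off-device, medication-changed ratings with on-device ones. The Stable Medication analysis checks only #6 to #11, so it would not cover the primary endpoint.
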